### 8.3.1 Primary efficacy assessments

The primary efficacy assessments will be LDL-C and discontinuation of statin therapy. Samples for LDL-C will be collected at screening (Visit 1) and on visit days 2, 3, 4, 5 and 6 (Table 8-1).

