1.1 Study design

The study design will be a randomized, two-arm, parallel-group, open-label, multicenter, clinical trial. Approximately 444 participants will be randomized 1:1 to "inclisiran first" implementation strategy or to usual care. Eligible participants have established ASCVD and elevated LDL-C (or non-HDL-C) despite treatment with maximally tolerated statin therapy (but without ezetimibe). The unit of randomization will be the participant. To address the bias that may arise due to differences in access to therapies, randomization will be stratified by [REDACTED] status, and various statistical methods will be adjusted for [REDACTED].

To minimize selection bias and increase generalizability of the results, potential study sites and potentially eligible participants will be identified using electronic data sets (EHR, claims and/or laboratory data). The goal in selecting study sites is to ensure a representative sample of sites in terms of geography, patient population, and lipid management practices. For example, the inclusion of specialized lipid clinics in the trial would lead to more intensive treatment than is typical and would therefore reduce the generalizability of the results. Several tactics will aim to enhance inclusion of minority and medically underserved populations, as these populations are traditionally underrepresented in clinical trials. [REDACTED]

[REDACTED] Second, investigators will explicitly be ority populations. Third, specific barriers to participation will be addressed, including rapid reimbursement (e.g., of transportation costs) and availability of trial materials (such as informed consent forms [ICFs]) in multiple languages). Selected sites will receive a list of patients who could qualify for the trial that is generated based on EHR, claims and/or laboratory data. All participants who meet the eligibility criteria are to be invited using a standardized invite.

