Study day will be calculated as (event date – study treatment start date + 1 day) for events that occurred on or after study treatment start date (e.g., visit, lab samples, AEs). For events prior to study treatment start date (e.g., time of diagnosis), study day will be negative and calculated as (event date – study treatment start date). Note that study treatment start date is study Day 1 and the day before study treatment start date is study Day -1 (i.e., no study Day 0).

Baseline and post-baseline definitions

In general, a baseline value refers to the last measurement available prior to administration of the first dose of study treatment (before or on study Day 1). A post-baseline value refers to a measurement taken after the first dose of study treatment (after study Day 1).

Lost to follow up

Participants whose study completion status is unclear because they fail to appear for study visits without stating an intention to withdraw.

On-treatment period

The period where the participants are exposed to the study treatment or usual care. For this study the planned treatment phase consists of 330 days.

Study Completer

Completers are defined as a participant who has a Subject Status of ‘completed’ on the Study Completion/Exit CRF page.

Analysis Visit Windows

The following analysis windows will be used for efficacy and safety analyses.

Table 2-2 Analysis Visit for Each Scheduled Visit

Analysis Visit	Target Study Day*	Analysis Window	
		From	To
Baseline	1		Before randomization/First Study Treatment
Day 90	91	1	135
Day 180	181	136	225
Day 270	271	226	300
Day 330	331	301	375

* Study Day 1 is being used to identify study treatment start date. When calculating study day, the target study day will correspond to the planned study day of the nominal visit. The analysis visit values (Baseline, Day 90, Day 180, Day 270, and Day 330) will be used for all presentations.

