2.5.2 Statistical hypothesis, model, and method of analysis

Primary efficacy variable 1

The null hypothesis is that the mean percent change from baseline in LDL-C at Day 330 for "inclisiran first" implementation strategy and usual care groups are equal. The alternative hypothesis is that the mean percent change from baseline in LDL-C at Day 330 for "inclisiran first" implementation strategy group is not equal to that of the usual care group.

Primary efficacy variable 1 will be analyzed using mixed-effects model repeated measures (MMRM) with treatment, visit (Day 90, Day 180, Day 270, Day 330), baseline, [REDACTED], [REDACTED], treatment-by-visit interaction, and baseline-by-visit interaction as explanatory variables. An unstructured covariance matrix will be assumed for this model. Least-squares mean of each treatment group, least-squares mean treatment difference, two-sided 97.5% confidence intervals for the treatments, two-sided 97.5% confidence interval for the treatment difference, and p-value based on the fitted MMRM will be reported for each applicable visit (day). If the p-value based on a two-sided test for treatment effect at Day 330 is < 0.025 and the corresponding least squares mean treatment difference ("inclisiran first" implementation strategy – usual care) is less than 0, statistical significance in favor of "inclisiran first" implementation strategy is shown. All efforts will be made to follow up participants until the end of the study. Participants will be expected to follow the visit schedule and assessments even after discontinuation of study treatment. Data after participants discontinued study treatment will be used in the analysis ("retrieved dropout").

The primary analysis of primary efficacy variable 1 will be based on the FAS. The primary analysis of this variable will be repeated for the Per-Protocol Set, Restricted Set 1, and Restricted Set 2.

Primary efficacy variable 2

The null hypothesis is that the difference ("inclisiran first" implementation strategy – usual care) in the proportion of participants who discontinue statin therapy at Day 330 is at least 0.15 (non-inferiority margin). The alternative hypothesis is that the difference ("inclisiran first" implementation strategy – usual care) in the proportion of participants who discontinue statin therapy at Day 330 is less than 0.15.

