2.7.3 Laboratory data

Laboratory values will be summarized by treatment group, including the observed value, changes and percent changes from baseline at each analysis visit (including Day 330/Last Visit). Fasting glucose parameter, when used in any analysis, will require the lab sample to be taken while fasting. Glucose values recorded under non-fasting conditions will not be used.

A shift analysis using the normal range (except for eGFR [REDACTED]) will be done which counts the number of participants with a low, normal or high value at baseline and a low, normal or high value post baseline.

The following ranges will be used for estimated Glomerular Filtration Rate (eGFR) [REDACTED]

- For eGFR, the categories will be Severe = <30 mL/min/1.73m²; Moderate = ≥ 30 to <60 mL/min/1.73m²; Mild = ≥ 60 to <90 mL/min/1.73m²; and Normal = ≥ 90 mL/min/1.73m².

[REDACTED]

The baseline and worst post-baseline value will be utilized for the shift tables. Note that the shift table dealing with the fasting glucose parameter will require the lab sample to be taken while fasting. Samples taken while the participant was not fasting will not be analyzed.

New onset of diabetes during the study will be identified by evaluating different components:

1) adverse events, [REDACTED]
[REDACTED] 3) initiation of antidiabetic medication. This analysis will only be conducted in participants who do not have diabetes at baseline (determined by either targeted medical history, prior concomitant therapies, [REDACTED] and fasting plasma glucose). Additionally, new onset or worsening of diabetes will be identified using SMQ and AE terms for diabetic treatment emergent adverse events (TEAEs). The analysis will be performed for all participants and then by baseline diabetes status.

A participant will be identified as being diabetic at baseline if ANY of the following conditions are met:

- Targeted medical history of diabetes (using targeted medical history CRF).
- Anti-diabetic medication (ATC level 2 code: A10) at baseline.
- [REDACTED] AND fasting glucose ≥ 126 mg/dL at baseline.

For this analysis, baseline fasting glucose uses the average of the last two assessments measured under fasting conditions at or prior to baseline. If only one fasting glucose value is available at or prior to baseline, the analysis will be based on the available data.

New onset or worsening of diabetes is defined if ANY of the following conditions [REDACTED]

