2.13 Interim analysis

After all participants complete their baseline visit, the demographic and baseline characteristics may be summarized to help design new studies. No analysis will be performed using post-baseline data. Thus, there is no need to adjust the level of significance for such interim analysis of baseline data.

3 Sample size calculation

The sample size was calculated for the two primary efficacy variables with adjustment for multiple testing by using the Bonferroni procedure.

For primary efficacy variable 1, i.e., percent change from baseline in LDL-C, the standard deviation is assumed to be 40, partly based on the results from ORION-10 and ORION-11 clinical trials, and considering that the standard deviation will likely be larger in this trial since

changes in lipid-lowering therapy are allowed in both treatment groups. An expected mean treatment difference of 15 is assumed, which is smaller than the mean difference observed in the Phase III trials, to account for 1) potential lower utilization of background lipid-lowering therapy in the "inclisiran first" implementation group compared to the usual care group, and 2) the ability to add non-statin lipid lowering therapy in the usual care group. [REDACTED]

Table 3-1 considers total sample sizes for expected mean treatment differences of 15, 20, and 25 and powers of 0.85 and 0.90 (nQuery Version 8.4.1.0). From Table 3-1, an expected mean treatment difference of 15 at Day 330 and a power of 0.90 were chosen to provide a total sample size of 354 participants.

Table 3-1 Same Size Calculations for Percent Change from Baseline in LDL-C

Mean treatment difference	Power = 0.85	Power = 0.90
15	306	354
20	172	200
25	112	128

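### The primary LDL-C model conditions on one pre-dose LDL-C and leaves the scheduled screening value unused; adding it as a covariate would gain a little precision for almost nothing

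*SAP*

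**What the plan says.** **Baseline.** SAP 2.1.1: "a baseline value refers to the last measurement available prior to administration of the first dose of study treatment". For LDL-C this is normally the Day 0 sample. It is the denominator of percent change and also the baseline covariate.

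**Model.** SAP 2.5.2 and Protocol 12.4.2 give an MMRM with treatment, visit, baseline, blacked-out text, treatment-by-visit and baseline-by-visit. The decision rule is that the "p-value based on a two-sided test for treatment effect at Day 330 is < 0.025", with the difference favouring the inclisiran strategy.

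**Available data.** Protocol 8.3.1: "Samples for LDL-C will be collected at screening (Visit 1", the sentence going on to list the later visits. Protocol Table 8-1 and SAP 1.1 confirm screening (Day -30 to -1) and Day 0 samples in both groups. Protocol Section 8 requires at least 8 hours of fasting for all visits, and Protocol 8.4.1 sends the samples to a central laboratory. The two pre-dose values are therefore comparable.

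**Sample size (SAP Section 3).** "the standard deviation is assumed to be 40", with "an expected mean treatment difference of 15 at Day 330 and a power of 0.90 were chosen" and "adjustment for multiple testing by using the Bonferroni procedure". No credit is taken for covariate adjustment.

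**The concern.** Day 0 LDL-C is measured with ordinary within-person variation. That variation enters percent change through the denominator, and the model adjusts only for the same noisy value. A second pre-randomisation value carries separate information on the participant's usual level, so conditioning on both should leave less residual variance than conditioning on one. What is at stake is the width of the confidence interval for the primary LDL-C effect and for absolute change in LDL-C. Bias, type I error and the estimand are not in question.

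**Working it through.** **1. Reproduce the planning figure.** Inputs from SAP 2.5.2 and Section 3: difference 15, SD 40, two-sided alpha 0.025, power 0.90.

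n per arm = 2(z₀.₉₈₇₅ + z₀.₉₀)² × SD² / difference² = 2 × (2.2414 + 1.2816)² × 1600 / 225 = 176.5, rounded up to 177. The total is 354, as stated.

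Primary variable 2 (both proportions 0.20, margin 0.15, one-sided 0.0125): 2 × 0.20 × 0.80 × (2.2414 + 1.2816)² / 0.15² = 176.5, so again 177 per arm and 354 in total. Allowing 20% for loss and statin intolerance, 354 / 0.80 = 442.5, against "Approximately 444 participants will be randomized 1:1".

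**2. Gain from the screening covariate.** The documents give no correlation between LDL-C values, so everything in this step is assumed. The simulation used:
- log-normal true LDL-C, median about 95 mg/dL before selection
- independent within-person error at screening, Day 0 and Day 330
- entry at screening LDL-C of at least 70 mg/dL
- a varying response, tuned so that percent change has SD 40

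Variance reduction = 1 − V(treatment, Day 0, screening) / V(treatment, Day 0), where V is the residual variance of a Day 330 linear model. This stands in for the MMRM contrast at that visit.

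| Between-person log-SD | Within 0.05 | 0.10 | 0.15 | 0.20 | 0.25 |
|---|---|---|---|---|---|
| 0.2 | 0.4% | 1.3% | 1.8% | 1.9% | 2.0% |
| 0.3 | 0.5% | 1.4% | 2.5% | 3.2% | 3.8% |
| 0.4 | 0.4% | 1.5% | 2.8% | 4.1% | 5.2% |

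Entering both values on the log scale raises the largest cell to 6.2%.

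With within-person log-SD 0.08 to 0.20 and between-person log-SD 0.25 to 0.33, simulations with different residual SDs gave:

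| Residual SD | Variance removed |
|---|---|
| near the planned 40, or somewhat above | about 1 to 2.5% |
| about 25 to 33 | about 2 to 4.5% |
| about 14 to 24 | about 6 to 9% |

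These are central ranges. The noisiest corner runs somewhat higher, as the 3.2% cell above shows. Absolute change gained about the same or slightly more.

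**3. What that buys.**
- Interval width: 1 − √(1 − 0.01) = 0.5%; 1 − √(1 − 0.025) = 1.3%; 1 − √(1 − 0.045) = 2.3%.
- With 10% loss only, 444 × 0.90 ≈ 400 are evaluable for LDL-C. The 97.5% half-width is 2.2414 × 40 × √(4/400) = 9.0 points. Narrowing it by 1.3% saves about 0.1 point.
- Power with 2% less variance: from 0.901 to 0.907 at 354 evaluable, and from 0.934 to 0.939 at 400.

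**4. What it costs.** Each visit's contrast loses about one degree of freedom: 1/400 = 0.25% and 1/354 = 0.28%, so about 0.3% of variance. The net gain at SD 40 is about 1 − 0.3 = 0.7% to 2.5 − 0.3 = 2.2%. At the lowest cell of the first table it is 0.4 − 0.3 = 0.1%, which is nothing of use.

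**The case against.** The strongest reply is that nothing is wrong. A single last pre-dose baseline with a baseline-by-visit term is coherent and valid, the sample size does not rely on adjustment, and the effect on power is under one percentage point at 2% less variance. All of that stands, and it is why this is a refinement only. The change would also touch a protocol-specified primary model in an open-label trial whose SAP is at final version 3.0, so it would have to be fixed and documented before lock.

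The blacked-out text is a weaker defence. Protocol 4.1.1 and SAP 1.1 and 2.5.5 suggest that it is the stratification factor, a yes/no status. If it did contain screening LDL-C, this point would fall away.

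A reader might infer more than the documents support:
- **A gain of 7 to 10%, or dozens of participants.** That size needs a residual SD of roughly 14 to 24. SAP Section 3 plans for 40 and expects more spread than in the earlier trials, because therapy changes are allowed in both groups.
- **A smaller trial.** Primary variable 2 needs 354 by itself.
- **No cost at all.** There is the lost degree of freedom. Also, if Day 0 is missing, the screening value becomes baseline and the two covariates coincide, so a rule is needed.
- **Benefit for every LDL-C secondary.** Secondary variables 4 to 7 are logistic models, where another prognostic covariate changes the conditional odds ratio being estimated. Variables 2 and 3 have their own linear models.
- **An inconsistency with glucose.** SAP 2.7.3 says "baseline fasting glucose uses the average of the last two assessments measured under fasting conditions", but only to classify diabetes at baseline for a safety summary. It sets no standard for the efficacy model.

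**Conclusion.** The point holds as an optional gain in precision. The plan conditions on one pre-dose LDL-C when two comparable ones are scheduled, and the second can be used without changing the endpoint, the estimand or the alpha. At the planned SD of 40 the expected gain is about 1 to 2.5% of residual variance, rising to about 4.5% if the SD is nearer 25 to 33, or about 0.5 to 2% off the interval width. These figures depend on assumed within-person log-SD 0.08 to 0.20 and between-person log-SD 0.25 to 0.33, and on a single-visit linear model in place of the full MMRM. The result would be valid and adequately powered without the change.

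**What to change.** Keep Day 0 LDL-C as baseline and as the denominator of percent change. Replacing or averaging the denominator would alter the endpoint and bring in a value that may have been used for eligibility, which is open to regression to the mean.

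Before database lock:
- Add screening LDL-C and screening-by-visit to the MMRM for percent and absolute change in LDL-C. Say that the terms apply to these LDL-C models only, because SAP 2.6.2 models secondary variables 8 to 21 on the primary analysis. State whether the supplementary MMRM in SAP 2.6.5 inherits them.
- Give a rule for participants with only one pre-dose LDL-C, for example setting the screening covariate to the available value.
- List the change in SAP Section 4.

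The cost is one extra parameter per visit (four in all), a short SAP edit and some programming. No visit, sample or participant is added, and primary variable 2 is untouched. If the sponsor prefers not to alter the primary model, the same terms could be pre-specified as a sensitivity analysis.

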Since inclisiran is commercially available in the US as of late-2021, utilization of it in the usual care group at the sole discretion of the treating physician will not be encouraged, but will also not be prohibited to avoid withholding of appropriate care. If treatment with a PCSK9-inhibiting monoclonal antibody was initiated and a patient would have to be transitioned to inclisiran, the PCSK9-inhibiting monoclonal antibody should be discontinued.

The collection of data from trial sites through eCRFs will be complemented with EHR data and claims data (e.g., lipid measurements and concomitant medications).

Participants randomized to “inclisiran first” implementation strategy group will receive inclisiran at Day 0, Day 90 and Day 270, consistent with the dosing regimen studied in the Phase III trials.

While study visits will be preferentially performed in-person at the study sites, phone or virtual visits are an acceptable alternative if in-person visits are not permitted or impractical due to a Public Health Emergency. Site or home health nursing service may be used to assist with blood draws and/or study medication administration if required at these visits. Informed consent forms will be available in English and Spanish.

Figure 3-1 Study Design

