## 8 Visit schedule and assessments

The Assessment Schedule ([Table 8-1](#)) lists the assessments when they are performed. All data obtained from these assessments must be supported in the participant’s source documentation.

Participants should be seen for all visits/assessments as outlined in the assessment schedule ([Table 8-1](#)) or as close to the designated day/time as possible (+/- 7 days). Missed or rescheduled visits should not lead to automatic discontinuation. Participants may be seen at

any time for an unscheduled visit, e.g., if they experience deterioration or AEs that in the opinion of the Investigator/qualified site staff requires closer monitoring.

Participants who discontinue from study treatment should continue to attend the remaining study visits as indicated in the Assessment Schedule ([Table 8-1](#)).

Participants who discontinue from study or withdraw their consent should be scheduled for a final evaluation visit if they agree, as soon as possible, at which time all of the assessments listed for the final visit will be performed. At this final visit, all investigational product should be reconciled, and the adverse event and concomitant medications not previously reported must be recorded on the eCRF.

Participants will have to comply with the following restrictions during the study:

- Participants need to fast for at least 8 hours for all visits (measurement of lipids/lipoproteins and blood glucose requires participants to be fasting). If the participant has not fasted, the collection of laboratory evaluations must be rescheduled.
- Blood donation will not be allowed at any time during the study

The “X” in the table denotes the assessments to be recorded in the clinical database or received electronically from a vendor. The “S” in the table denotes the assessments that are only in the participant’s source documentation and do not need to be recorded in the clinical database.

As per [Section 4.6](#), during a Public Health Emergency that limits or prevents on-site study visits, alternative methods of providing continuing care may be implemented by the Investigator as the situation dictates. If allowable by a local Health Authority and depending on operational capabilities, phone calls, virtual contacts (e.g. tele consult) or visits by site staff/ home nursing staff to the participant’s home, can replace on-site study visits, for the duration of the disruption until it is safe for the participant to visit the site again.

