#### **8.4.1 Laboratory evaluations**

Specimens will be obtained at the time points in the Assessment Schedule ([Table 8-1](#)).

A central laboratory will be used for analysis of all specimens collected, with the exception of urine pregnancy tests and urine dipstick tests, which will be done locally (using testing materials supplied by the central laboratory). Serum pregnancy tests at screening will be done by the central laboratory. Details on the collections, shipment of samples and reporting of results by the central laboratory are provided to investigators in a Laboratory Manual.

Clinically significant abnormalities must be recorded as either medical history/current medical conditions or adverse events as appropriate.

Clinically notable laboratory findings are defined in [Section 16.1](#)

Local laboratory assessments may be performed on an as-needed basis for unscheduled visits. Laboratory values that exceed the boundaries of a notable laboratory abnormality must be commented on by the investigator on the source document and additional laboratory evaluations should be performed, as judged appropriate by the investigator. If the laboratory abnormality induces clinical signs or symptoms, or requires therapeutic intervention, then the diagnosis or medical condition must be entered on the patient's AE eCRF. If the laboratory abnormality is the primary reason for an unforeseen hospitalization or otherwise fulfills the seriousness category of an AE, then the procedure for rapid notification of SAEs must be followed. Likewise, if the laboratory abnormality leads to discontinuation from the study drug (temporarily or permanently), the patient must be followed until the abnormality resolves or until it is judged to be permanent. This investigation may include continued monitoring by repeat laboratory testing or by performing additional laboratory tests as deemed necessary by the investigator or the Novartis medical monitor.

As per [Section 4.6](#), during a Public Health Emergency that limits or prevents on-site study visits, if a visit by site staff/home nursing staff is arranged, specimen samples should be collected during the visit and processed and handled in line with the study laboratory manual.

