Data collected at scheduled or unscheduled visits will be used in the analysis if they fall into an analysis window for an analysis visit. If more than one visit (scheduled or unscheduled) is made within the window specified above for any analysis visit, the non-missing assessment closest to the target study day will be used in the analysis for that visit. In the case of tied visits, non-missing data from the later visit will be used. In the case of identical collection dates and times, the average of the two visits will be used. However, all data will be included in the participant data listings.

Last Visit Summaries

The protocol uses the term End of Study (EOS) for Day 330. If a participant discontinues from the study early, they will have an early termination visit that is before Day 330. Using the windowing provided in [Table 2-2](#), the early termination visit will be assigned to the nearest analysis visit. Tables that summarize data by visit will include data by analysis visit (Baseline, Day 90, Day 180, Day 270, and Day 330) along with a Day 330/Last Visit which will combine data from Day 330 for those participants who have data collected within the Day 330 analysis window with the data from the last post-baseline visit for those participants who do not have data collected in the Day 330 analysis window.

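### The SAP picks the LDL-C value in each visit window by closeness to the target day alone, so an unscheduled value, possibly from a local laboratory, can displace the scheduled fasting central-laboratory sample in the primary analysis.

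*SAP*

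**What the plan says.** SAP 2.1.1 introduces its windows with the words "The following analysis windows will be used for efficacy and safety analyses", so they govern the LDL-C mixed model in SAP 2.5.2. Eligibility is broad: "Data collected at scheduled or unscheduled visits will be used in the analysis if they fall into an analysis window for an analysis visit". When a window holds several values, "the non-missing assessment closest to the target study day will be used in the analysis for that visit", and "In the case of tied visits, non-missing data from the later visit will be used". Two results with the same date and time are averaged. Table 2-2 gives the Day 330 window as study days 301 to 375 with target day 331, and opens the Day 90 window at study day 1.

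On the source of the values, Protocol 8.4.1 sends study specimens to a central laboratory, apart from urine pregnancy and dipstick tests, but adds: "Local laboratory assessments may be performed on an as-needed basis for unscheduled visits". Protocol 3 and SAP 1.1 both say that case report form data will be "complemented with EHR data and claims data (e.g., lipid measurements and concomitant medications").

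On fasting, Protocol 8 asks for at least 8 hours before every visit, naming lipids and glucose, and says: "If the participant has not fasted, the collection of laboratory evaluations must be rescheduled". The SAP carries this into the analysis for one analyte only, in 2.7.3: "Glucose values recorded under non-fasting conditions will not be used".

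**The concern.** LDL-C at Day 330 is a primary variable, yet the rule that chooses which LDL-C value is analysed ignores whether it came from the scheduled visit, which laboratory measured it and whether the participant had fasted. I found no filter in SAP 2.5.1, 2.5.2, 4 or 5.2 that closes the gap. A protocol-standard sample taken a few days off target therefore loses to any eligible value that is nearer.

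The first thing at stake is measurement consistency: assay and fasting differences would add noise to LDL-C, and also to triglycerides and VLDL-C. The second is comparability. The trial is open-label and routine care belongs to the treating physician, so extra testing could differ between arms. The third is pre-specification. If the SAP does not say which sources are eligible, that choice falls to whoever programs the derivation.

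There is also a small inconsistency in the same section. A post-baseline value is one taken after study day 1, but the Day 90 window includes day 1.

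**Working it through.** **1. Design figures, reproduced.** Inputs from SAP 3: difference 15, SD 40, power 0.90; two-sided alpha 0.025 from SAP 2.5.2.

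n per arm = 2 × (2.2414 + 1.2816)² × (40/15)² = 176.5, rounded up to 177, so 354 in total. This matches Table 3-1. Exact power at 177 per arm, from the noncentral t distribution, is 0.899. No stated figure is in dispute; this only fixes the reference for step 4.

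**2. How far the rule reaches.** Let the scheduled Day 330 sample be k days from day 331, with k at most 7 under the visit tolerance in Protocol 8. The number of days strictly closer to target is 2k − 1 for k ≥ 1, and none for k = 0. That gives 1 day at k = 1, 5 at k = 3 and 13 at k = 7.

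**3. Chance of displacement.** Assumptions that are not in the documents: the participant has one extra eligible test, on a random day of the 75-day window (375 − 301 + 1), and the scheduled visit is equally likely on each of the 15 days from 324 to 338.

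- Closer days summed over k = 1 to 7: 1 + 3 + 5 + 7 + 9 + 11 + 13 = 49 on each side of target.
- Counting both sides: 98/(15 × 75) = 98/1125 = 8.7%.
- Day 330 is the end-of-study visit. If it falls early, every closer day lies after it. Counting only tests before the visit leaves the late-visit side: 49/1125 = 4.4%. Ties add nothing here, because the later of two tied values is then the scheduled one.
- If 30 to 50% of participants had such a test (assumed), 1.3 to 2.2% of Day 330 values would change source (0.30 × 4.4% to 0.50 × 4.4%).

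The 4.4% keeps all 75 days in the denominator, so a test after the visit counts as harmless. If the test is instead assumed to fall between day 301 and the day before the visit, there are 30 + k candidate days for a visit k days late. The chance is then (1/31 + 3/32 + 5/33 + 7/34 + 9/35 + 11/36 + 13/37)/15 = 9.3%, or 2.8 to 4.7% of Day 330 values at the same testing rates.

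**4. What that could do to the result.** Suppose a fraction f of one arm's Day 330 values is replaced, with a mean bias of b percentage points toward no difference (both assumed). The treatment difference shifts by f × b.

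| f | b | shift (of 15) | power at 177 per arm |
|---|---|---|---|
| 2% | 5 | 0.1 | 0.894 |
| 2% | 10 | 0.2 | 0.890 |
| 5% | 5 | 0.25 | 0.888 |
| 5% | 10 | 0.5 | 0.876 |
| 10% | 10 | 1.0 | 0.850 |
| 20% | 10 | 2.0 | 0.787 |

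With no bias and an added SD of 20 in the replaced values, power stays at 0.891 or above even at f = 20%. Step 3 puts f between about 1% and 5%, so the last two rows would need replacement well beyond those assumptions.

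**The case against.** The strongest reply is that the planned LDL-C samples are already controlled. Protocol 8.3.1 ties the primary LDL-C assessment to the scheduled visits and Protocol 8.4.1 sends specimens to a central laboratory. The sentence permitting local laboratories sits in the safety section, next to text on notable abnormalities and adverse events, and nothing plans local LDL-C testing. This stands as a statement of intent and is a good reason to expect few displaced values. It does not change the selection rule, which admits unscheduled data for efficacy and ranks only by distance.

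A reader might infer that routine lipid tests in health records will flow into the primary model. The documents do not say so. They name such measurements as a complement to the case report form, Protocol 11.1 makes direct capture conditional, and the window rule speaks of visits. The defensible statement is that eligibility is left unstated.

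A reader might also infer that non-fasting lipids are accepted. Protocol 8 requires fasting at all visits, unscheduled ones included, so fasting is controlled at collection. The gap concerns values that nevertheless arrive non-fasting, or come from outside study visits: the SAP says what to do with them for glucose and not for lipids.

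Finally, one might infer bias between the arms. Protocol 3 gives both arms equal numbers of visits and blood draws and returns study LDL-C results to physicians in both, which reduces the need for extra tests. Differential testing is plausible in an open-label trial but is not shown.

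**Conclusion.** The point holds as a gap in the derivation of a primary variable, with a small likely effect. As written, an unscheduled value, which may be a local-laboratory result, can displace the scheduled fasting central sample. The SAP leaves the eligibility of health-record lipids open and states a fasting filter for glucose only.

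For size, about 4% of extra tests would displace the Day 330 sample, given one test at a random day of the window, visits within 7 days of target, and only tests before the end-of-study visit counting. The figure is about 9% if the test is assumed to precede the visit. The testing rate and any bias are assumptions; the documents give neither. With up to 5% of one arm's values replaced and a bias of up to 10 points, the difference moves by no more than 0.5 of 15 points. That does not threaten the primary conclusion.

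The breadth of the Day 90 window might suggest that it should open much later, for example at Day 46. That does not follow. No visit is scheduled between baseline and Day 90, a very early value is used only when nothing nearer exists, and SAP 2.1.1 assigns early-termination visits to the nearest analysis visit. A later start would drop the only post-baseline value of very early leavers. The one clear correction there is Day 1 to Day 2.

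**What to change.** In SAP 2.1.1, for the lipid efficacy variables:

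- Within each window, use the scheduled-visit fasting central-laboratory value first.
- Use an unscheduled, local or health-record value only if no such value exists, and flag it in the analysis dataset.
- Exclude lipid values known to be non-fasting from the lipid efficacy analyses, as the SAP already does for glucose.
- Add a sensitivity analysis of primary efficacy variable 1 limited to scheduled central-laboratory samples.
- In Table 2-2, change the lower bound of the Day 90 window from Day 1 to Day 2, to agree with the definition of post-baseline.

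The cost is SAP wording, a change of sort order in the derivation and one extra model run; no new data are needed. The downside is that the value analysed may lie a few days further from the target day, by at most 7 days from target when the visit meets the protocol tolerance. The change should be made before database lock.
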